Student Research Project Proposal

Title:

Carbon Dioxide (CO₂) Clearance from various face masks in Normal Volunteers at various level of Expiratory Positive Airway Pressure (EPAP) when Using a Non-Invasive Positive Pressure Ventilation (NIPPV)

Investigators:

Mentor:

[name], MHS, RRT, FAARC, FCCP

Graduate Student:

[name], Respiratory Care Department, Rush University.

Study aim:

Determine the EPAP (baseline pressure) required to effectively wash out CO₂ for current available masks, and assess perceived level of comfort with each mask with using noninvasive ventilator.

1- Abstract:

Background: Noninvasive positive pressure ventilation (NIPPV) can be delivered via single limb circuit or double limb circuit ventilators. There are many advantages to NPPV. However, a reasonable number of questions remain unanswered, such as mask impact on carbon dioxide (CO₂) clearance based on EPAP level.

Objective: Determine the EPAP (baseline pressure) required to effectively wash out CO₂ for each mask, and assess perceived level of comfort with each mask with ICU ventilator.

Method: This study will be a randomized crossover trial that will be conducted at Rush University. The study will be conducted with 20 healthy volunteers who will be placed on ICU ventilator operating in the NIPPV mode. All subjects will perform 15 minutes of breathing on NIPPV on each mask of the 4 different masks (2 oronasal and 2 full face masks) that are randomly selected. Breathing through each mask will be followed by a 5-minute wash out period between masks. End tidal Carbon Dioxide (EtCO₂) will be sampled nasal/oral. Different levels of EPAP will be set and CO₂ clearance will be monitored. Additionally, subjective mask comfort will be assessed via visual analog scale (VAS) with 1 referring to least comfortable and 5 being the most comfortable.

2- Introduction

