via EtCO₂. Masks B & C both had higher rate of total leaks due to higher rate of unintentional leaks which may improved CO₂ wash out, hence, led to no differences in PtcCO₂.⁸ Another study compared total face mask against oronasal mask impact on gas exchange (PvCO₂) favors total face mask in the first 6 hours and during the acute phase of respiratory failure using NIPPV.⁷ Both Medrinal and Sadeghi assessed gas exchange not masks' CO₂ clearance. Since the intentional leak impacts CO₂ clearance, and the intentional leak level depends on the level of pressure.⁸ The previous studies didn't study different level of EPAP (baseline pressure). One level of EPAP pressure of 4 cm H₂O was used in Medrinal study based on Samolski's finding.⁸ While in Sadeghi's study, IPAP started at 10 cm H₂O and EPAP started at 4 cm H₂O. IPAP and EPAP were increased gradually based on subjects' need, therefore it lacked consistency in EPAP level.⁹

ICU ventilators using double limb circuit is an alternative to deliver NIPPV, however, researches on minimum baseline pressure required to prevent CO₂ rebreathing is not clear as well. In a study that compared 3 types of masks (2 ONM and 1 FFM) to helmet in acute hypercapnia respiratory failure. NIPPV in both group improved arterial blood gases. ICU ventilators settings in masks group used positive end expiratory pressure (PEEP) referring to baseline pressure that ranged from 3 – 5 cm H₂O (mean 4.26 ± 1.92); and inspiratory pressure adjusted to achieve tidal volume of 6-8 ml/kg (16.37 ± 4.19). On the other hand, settings for helmet groups were ~ 30%.¹¹

The answer regarding effective EPAP level to wash out CO₂ remains uncertain. The purpose of this study is to compare the efficacy of CO₂ clearance between different NIPPV interfaces (oronasal and full face masks) when using double limb circuit ICU

ventilator at lower levels of EPAP. The aim of this study is to determine the EPAP (baseline pressure) required to effectively wash out CO₂ for each mask and assess perceived level of comfort with each mask.

3- Methods:

This study will be a randomized crossover trial that will be conducted at Rush University.

Normal volunteers will be recruited from Rush University Medical Centers. Volunteers will be screened with inclusion and exclusion criteria and an informed consent is required in order for them to participate. Demographic (age, gender, ethnicity) will be obtained.

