Also, initial baseline vital signs (heart rate, blood pressure, respiratory rate, and oxygen saturation) will be obtained. EtCO₂ will be obtained at baseline and periodically using an oral/nasal sample line with the CapnostreamTM 20p monitor (Medtronic, Minneapolis, MN). The study will use a double limb circuit ICU ventilator Puritan BennettTM (Medtronic, Dublin, Ireland).

We will evaluate 4 NIPPV masks (2 oronasal masks and 2 full face masks).

[figure not shown]
Oronasal masks will be labeled as group A and numbered as A1 and A2; while full face masks will be labeled group B and numbered as B1 and B2. Order of the masks will be randomly chosen in two steps. First steps will be choosing A or B then randomly assign mask in each of these groups. We will randomly assign mask in group A or B by drawing an initial mask from the group and then continue the sequence of masks from that point.

For example, we randomly chose group A, then randomly chose A2, the sequence will be A2, A1. Then we would randomly choose B2, then the sequence would be B2, B1.

All subjects will perform 15 minutes on each mask followed by 5 minutes wash out interval between masks. EPAP levels will be 0, 2, 4, & 5 while IPAP remains at 5 higher than EPAP. EtCO₂ will be collected at 4:00, 4:30 and 5:00 minute mark. These three measures should differ by less than 20% of their average. Also, subjective mask

comfort will be assessed via visual analog scale (VAS) with 1 referring to least comfortable and 5 being the most comfortable after 5 each EPAP setting.

Procedure figure:

4- Subject Population:

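### The 5-minute washout has no stated EtCO₂ check before each mask, and the analysis has no baseline, period or carry-over term, so residual CO₂ or session drift could go unrecognised

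*Combined protocol and SAP*

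**What the plan says.** - **Design.** Section 3 (Methods): "This study will be a randomized crossover trial that will be conducted at Rush University". Each of the 20 volunteers (section 4.2) wears all four masks, two oronasal (group A) and two full face (group B). Order is drawn in two steps: first the group, then the starting mask within each group.
- **Washout.** Methods: "All subjects will perform 15 minutes on each mask followed by 5 minutes wash out interval between masks". The Abstract agrees: "Breathing through each mask will be followed by a 5-minute wash out period between masks". Neither place gives a return-to-baseline criterion.
- **Baseline.** Methods: "initial baseline vital signs (heart rate, blood pressure, respiratory rate, and oxygen saturation) will be obtained". For the outcome itself: "EtCO₂ will be obtained at baseline and periodically using an oral/nasal sample line". The second word of timing there is not tied to the end of a washout.
- **Pressure settings.** Methods: "EPAP levels will be 0, 2, 4, & 5 while IPAP remains at 5 higher than EPAP". The order in which the EPAP levels are applied is not stated.
- **Timed readings.** The only clock times given for the outcome are these: "EtCO₂ will be collected at 4:00, 4:30 and 5:00 minute mark". An agreement rule for the three readings is then added: "These three measures should differ by less than 20% of their average".
- **Analysis.** Section 12 compares EtCO₂ across EPAP levels, and comfort across masks, by Kruskal-Wallis tests with Mann-Whitney follow-up. It names no baseline, period, sequence or carry-over term.
- **Purpose.** The end of the Introduction sets out to compare CO₂ clearance between interfaces and to find the EPAP each mask needs.

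**The concern.** In a crossover, the washout is what allows each mask's readings to be attributed to that mask. Here the next mask starts when five minutes have passed, whatever EtCO₂ is doing, and nothing in the readable text requires anyone to look. If EtCO₂ has not settled, in either direction, the first setting on the next mask begins displaced.

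Two results are exposed. One is the set of per-mask EtCO₂ values, which must carry the stated purpose. The other is the planned EPAP comparison. If the levels are applied as listed, the first setting is always EPAP 0, and randomising masks does nothing to spread a residual across EPAP levels.

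The agreement rule for the three readings does not fill the gap. It checks that they are close to one another, not that they are free of a residual.

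**Working it through.** The plan gives no carry-over figure, time constant or expected rise, so there is nothing of its own to reproduce. The inputs from the documents are: 4 masks, 15 minutes per mask, 5 minutes' washout, readings at 4:00, 4:30 and 5:00, 4 EPAP levels, and 20 volunteers. The assumed inputs are a first-order return with time constant τ of 1-10 minutes, a 5 mmHg rise at mask removal, and a resting EtCO₂ of 38 mmHg.

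**1. Timing.** Taking the reading times as minutes into each EPAP setting, the first reading comes 5 + 4 = 9 minutes after the previous mask. Four settings read to 5:00 need 4 × 5 = 20 minutes, but 15 are stated (15/4 = 3.75 minutes per setting, before the 4:00 reading). The start of mask 4 falls 3 × 15 + 3 × 5 = 60 minutes into the session, or 3 × 20 + 3 × 5 = 75 minutes with 20-minute periods. That is the age of any initial baseline by then.

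**2. Residual share, exp(−t/τ).**

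| τ (min, assumed) | End of washout (5 min) | First reading (9 min) | First reading after a 5 mmHg rise |
|---|---|---|---|
| 1 | 0.7% | 0.01% | 0.00 mmHg |
| 2 | 8% | 1% | 0.06 mmHg |
| 3 | 19% | 5% | 0.25 mmHg |
| 5 | 37% | 17% | 0.83 mmHg |
| 10 | 61% | 41% | 2.03 mmHg |

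With 5-minute settings the 4:00 readings fall at 9, 14, 19 and 24 minutes. Averaged over the four settings, a 5 mmHg rise leaves 5 × (0.0498 + 0.0094 + 0.0018 + 0.0003)/4 = 0.08 mmHg at τ = 3. At τ = 5 it leaves 5 × (0.1653 + 0.0608 + 0.0224 + 0.0082)/4 = 0.32 mmHg.

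**3. Does randomised order remove it?** The two-step draw gives 8 sequences.
- *Position.* Each mask has probability 1/4 of each position, so additive drift cancels between masks in expectation. With 20 unrestricted draws, a group-order split of 14:6 or worse has probability 0.115.
- *Predecessor.* Each mask follows its group mate with probability 1/2, each mask of the other group with probability 1/8, and nothing with probability 1/4. Writing λ for the carry-over left by each mask type, the expected bias in full face minus oronasal is (0.5 λ_B + 0.25 λ_A) − (0.5 λ_A + 0.25 λ_B) = 0.25 (λ_B − λ_A). Per 1 mmHg difference at mask removal, the first-setting bias is 0.25 × exp(−9/τ): about 0.00, 0.003, 0.012, 0.04 and 0.10 mmHg at τ = 1, 2, 3, 5 and 10.

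**4. EPAP comparison, if the listed order is used.** Of the 20 × 4 = 80 first settings, 20 × 3 = 60 follow a washout, so 75% of EPAP 0 readings would carry a residual. After a 5 mmHg rise, the EPAP 0 mean shifts by 0.75 × 5 × exp(−9/τ): 0.04 mmHg at τ = 2, 0.19 at 3, 0.62 at 5 and 1.52 at 10.

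**5. The 20% rule.** At 38 mmHg it allows a spread of 0.20 × 38 = 7.6 mmHg. A decaying 5 mmHg excess moves the three readings by only 0.2-0.5% of their mean (τ = 3-10), so the rule cannot reveal it.

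**The case against.** The case against is substantial, and much of it stands.

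- *A reader might infer that one initial baseline serves all four masks.* The documents do not establish this. The word initial is attached to the vital signs; EtCO₂ is also taken periodically; the procedure figure is not shown; and no planned analysis uses a baseline at all. What can be said is that the readable text specifies no pre-mask EtCO₂ reading.
- *A reader might infer that leftover CO₂ or drift is charged to the next mask.* This is possible but not shown. Mask position is balanced in expectation, carry-over common to all masks cancels in expectation, and the bias in the mask-type contrast is small unless the time constant is long. If the levels do run as listed, each mask comes off at the highest EPAP, where any rise may be least.
- *A reader might infer that a planned EtCO₂ mask test is biased.* Section 12 contains no such test. The exposed results are the per-mask EtCO₂ summaries and the EPAP comparison.
- *A reader might infer that nothing could be recovered afterwards.* That is too strong. If the drawn order is kept, period and previous-mask effects can be estimated, though section 12 does not plan it and 20 volunteers give limited precision.
- *The 5-minute break has a precedent.* The Introduction describes a volunteer study with the same break and no transcutaneous CO₂ difference between masks. It used 10-minute periods at a single EPAP of 4, and no check of the break is reported, so it neither validates nor refutes the choice here.

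The objection does not remove the core: no timed check of the washout is stated, and no planned term would pick up its failure.

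**Conclusion.** The point holds in a limited form. The readable text fixes the washout by the clock, specifies no EtCO₂ reading before each mask, and plans no baseline, period or carry-over term. Residual CO₂ or drift could therefore go unrecognised in the per-mask EtCO₂ results. Under the listed EPAP order it would fall mainly on EPAP 0.

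The size cannot be settled from the documents. At the first readings it ranges from negligible (time constant 1-2 minutes) to 41% of any rise (10 minutes). The 5 mmHg rise is only illustrative, and a residual could equally be low. Drift is mainly added noise. These results assume a first-order return and readings timed within each EPAP setting. This is a cheap improvement to a sound basic design, not evidence that the mask comparison is biased.

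**What to change.** 1. Leaving the washout length as it is, record EtCO₂ with the existing monitor over the last 30 seconds before each mask is applied. If the procedure figure already shows such a reading, say so in the text.
2. Analyse EtCO₂ in a mixed model with volunteer as a random effect and terms for mask, EPAP, period and the pre-mask value. Kruskal-Wallis and Mann-Whitney tests take no covariate, so this replaces the EtCO₂ analysis in section 12. Use the pre-mask value as a covariate rather than subtracting it: a residual shrinks further before the readings, so subtraction would over-correct.
3. Report how many of the 60 washouts (20 × 3) ended away from the volunteer's initial EtCO₂ by more than a margin fixed in advance.
4. Do not drop first-setting data as the main remedy. If done at all, label it a sensitivity analysis, because it may remove mostly EPAP 0 readings.
5. State the order in which EPAP levels are applied, and reconcile the 15 minutes per mask with four settings read to 5:00.

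**Cost.** Three extra readings per volunteer, since the baseline precedes the first mask; reapplying the sampling line if it comes off during washout, which the text does not say; one data field; and a few model degrees of freedom. The covariate may also reduce residual variance by r², that is 0.3² = 9% to 0.6² = 36% at assumed within-volunteer correlations of 0.3-0.6. The documents do not support any particular value.

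### Fifteen minutes per mask cannot hold four EPAP levels if each runs to its 5:00 EtCO₂ reading; at least 20 minutes are needed

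*Combined protocol and SAP*

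**What the plan says.** Two places give the time on each mask. The abstract (Section 1) says "All subjects will perform 15 minutes of breathing on NIPPV on each mask of the 4 different masks" and adds "Breathing through each mask will be followed by a 5-minute wash out period between masks". Section 3 (Methods) repeats it: "All subjects will perform 15 minutes on each mask followed by 5 minutes wash out interval between masks".

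Section 3 then describes what happens on the mask:

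- Pressure settings: "EPAP levels will be 0, 2, 4, & 5 while IPAP remains at 5 higher than EPAP".
- Timed readings: "EtCO₂ will be collected at 4:00, 4:30 and 5:00 minute mark".
- Agreement rule for those readings: "These three measures should differ by less than 20% of their average".
- Comfort, on a scale with "5 being the most comfortable after 5 each EPAP setting". A unit seems to be missing after the second 5.

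Baseline measurement is described separately, next to the baseline vital signs: "EtCO₂ will be obtained at baseline and periodically using an oral/nasal sample line".

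The aim, at the end of Section 2, is to find the EPAP that clears CO₂ effectively for each mask. Section 12 (Analysis) compares EtCO₂ across EPAP levels. No text gives a duration per EPAP level, and none says whether the reading clock restarts when the level changes.

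**The concern.** The mask time and the list of measurements do not appear to fit together. If every level is run on every mask and each is held until its third reading, the time needed exceeds the time allotted.

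This matters because EtCO₂ by EPAP level is one of the two planned comparisons and the core of the study aim. Staff who keep to 15 minutes would have to leave out a level, and the text does not say which, or shorten every level so that no scheduled reading is reached. Staff who run all the levels in full would keep volunteers on each mask longer than the protocol states. The text does not say which statement prevails.

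**Working it through.** **Inputs**

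- Time on each mask: 15 min (abstract and Section 3).
- EPAP levels: 4, namely 0, 2, 4 and 5 (Section 3).
- First and last timed readings: 4:00 and 5:00 (Section 3).
- Masks per volunteer: 4 (abstract and Section 3).
- Washout: 5 min between masks (abstract and Section 3).

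**Does the clock restart at each level?** The protocol does not say so, so this is an inference. Four features support it:

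1. Comfort is rated at each EPAP setting, and the stray 5 in that sentence matches the 5:00 reading.
2. A rule that three readings 30 seconds apart must agree within 20% of their average makes sense for repeats at one steady setting.
3. The aim is to find the required EPAP for each mask, which needs EtCO₂ at several levels on each mask.
4. Section 12 analyses EtCO₂ by EPAP level.

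The alternative is one set of readings per mask. That would give timed EtCO₂ at only one level on each mask and leave minutes 5 to 15 with no specified reading.

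**Can the stated 15 minutes be reproduced?** Minimum time per mask = number of levels × time each level is held.

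| Schedule | Calculation | Result |
|---|---|---|
| Four levels, each to the last reading | 4 × 5 | 20 min |
| Four levels, each stopped at the first reading | 4 × 4 | 16 min |
| 15 min split equally over four levels | 15 / 4 | 3.75 min = 3:45 per level |
| Three levels, each to the last reading | 3 × 5 | 15 min |

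Only the last row gives 15, and it omits a listed level. The equal split ends 4:00 − 3:45 = 15 seconds before the first reading. None of these sums allows time to change settings or record comfort.

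**Can time be found elsewhere?**

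- *EPAP 0 as an off-mask baseline.* Section 3 lists EPAP 0 with the other levels and sets IPAP 5 above EPAP, so it is a ventilated setting with IPAP 0 + 5 = 5. Baseline EtCO₂ is described separately.
- *The washout.* It lies between masks, so it adds no time on a mask.

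**Size**

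- Shortfall per mask: 20 − 15 = 5 min, the length of one level.
- Shortfall per volunteer: 5 × 4 = 20 min.
- Mask time per volunteer: 4 × 20 = 80 min, against 4 × 15 = 60 min.
- Mask time plus three washouts: 80 + 3 × 5 = 95 min, against 60 + 3 × 5 = 75 min.

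The totals per volunteer are sums made here; the protocol states none.

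**The case against.** The strongest reply is that the conflict depends on a schedule the text never sets out. No duration per level is given, nothing says that the clock restarts, and the most direct support is a sentence with a word missing. The procedure figure announced at the end of Section 3 is where the timing would be expected, and it was not available. It might show 20 minutes per mask, in which case 15 is a slip that staff following the figure would not act on.

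A second point concerns the remedy. Fifteen minutes appears twice, the list of four levels appears once, and 15 minutes is exactly three 5-minute levels. The error could therefore lie in the number of levels.

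Third, the practical harm may be small. The mismatch would show on the first mask of the first volunteer, and the natural response is to finish the levels, at a cost of about 20 extra minutes for a healthy volunteer. No sample size or test in the plan depends on the 15-minute figure.

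Much of this is fair as a limit on the point. The restart is inferred, the figure could settle what was intended, and an overrun loses no data. It does not remove the conflict. No figure can fit four 5-minute levels into 15 minutes, and if the figure shows something else the text still needs correcting. The three-level reading has no support beyond the arithmetic match, because nothing takes any listed level off the mask. A single set of readings per mask would not serve the aim.

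**Conclusion.** The concern holds. With four EPAP levels run on each mask and readings timed from the start of each level, at least 20 minutes per mask are needed and the protocol gives 15. The gap is 5 minutes per mask and 20 minutes per volunteer.

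The conclusion rests on two assumptions: that all four listed levels are run on every mask, and that the reading clock restarts at each level. Both are inferred, and both fit the aim and the analysis better than the alternatives. The arithmetic itself is exact.

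The consequence depends on what staff do. If they hold to 15 minutes, only three of the four levels fit, or all four end before any scheduled reading. If they overrun to 20 minutes, the data are complete and the only effect is more mask time than the protocol gives. This is an operating figure to correct before enrolment; it does not undermine the design.

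**What to change.** - Change 15 to 20 minutes per mask in the abstract and in Section 3. This keeps every listed level.
- State in Section 3 that the readings at 4:00, 4:30 and 5:00 are timed from the start of each EPAP level.
- Complete the comfort sentence so that the rating is made after 5 minutes at each EPAP setting. Minutes is this review's reading of the missing unit, so the investigator should confirm it.
- Check that the procedure figure shows the same timing.

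If only three levels per mask were intended, the protocol should say so and name them; 15 minutes would then be enough for the readings.

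The cost is two numbers and two sentences of wording, plus about 20 more minutes of mask time per volunteer than the text now implies.

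### Fifteen minutes per mask cannot hold four EPAP levels each read to 5:00; and if the levels run in listed order on every mask, EPAP cannot be separated from time on mask

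*Combined protocol and SAP*

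**What the plan says.** **Time per mask.** Section 3 (Methods): "All subjects will perform 15 minutes on each mask followed by 5 minutes wash out interval between masks". The Abstract gives the same figure: "All subjects will perform 15 minutes of breathing on NIPPV on each mask".

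**Levels and readings.** Section 3: "EPAP levels will be 0, 2, 4, & 5 while IPAP remains at 5 higher than EPAP". On timing within a mask, the same section says that the EtCO₂ measurement "will be collected at 4:00, 4:30 and 5:00 minute mark", and the three values should agree to within 20% of their average. Comfort is scored from 1 to 5, the top score "being the most comfortable after 5 each EPAP setting". The unit after the 5 in that last quote is missing; I read it as minutes.

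**Order.** For masks, section 3 gives a rule with a worked example: "Order of the masks will be randomly chosen in two steps". For EPAP it only lists the four values, and the Abstract says only "Different levels of EPAP will be set". Section 3 ends with a procedure figure that is not shown in the text available here.

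**Analysis.** Section 12 compares EtCO₂ across EPAP levels by Kruskal-Wallis, then Mann-Whitney, with no term for time or order. Section 11 lists one limitation, that the subjects are healthy.

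**The concern.** The study aim is the EPAP needed to clear CO₂ for each mask, so the comparison between EPAP levels within a mask carries the main result. Two features of the schedule bear on it.

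First, the stated mask time looks too short for the stated readings. Staff would then have to drop a level, shorten the slots so that readings are missed, or overrun. Different choices on different days would leave EtCO₂ values that are not comparable.

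Second, if every mask runs through the levels in the same ascending order, EPAP level and position within the mask are the same variable. EtCO₂ that falls with time on mask would look like a benefit of higher EPAP, and EtCO₂ that rises would hide one. Randomising the masks does not help, because each mask repeats the same sequence.

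**Working it through.** **Inputs.** From section 3 and the Abstract: 20 subjects, 4 masks, 4 EPAP levels, 15 minutes per mask, 5 minutes between masks, last EtCO₂ reading at 5:00. Assumed: the reading clock restarts at each level, slots last 5 minutes, and drift sizes are as given below. The documents give no drift and no standard deviation.

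**1. Timing**

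- Needed to the last reading: 4 × 5 = 20 minutes, against 15 stated; the shortfall is 5 minutes per mask.
- Levels that fit: 15 / 5 = 3.
- Equal split: 15 / 4 = 3.75 minutes per level, before the 4:00 reading.
- Stopping each level at its first reading: 4 × 4 = 16 minutes, still more than 15.
- Session as stated: 4 × 15 + 3 × 5 = 75 minutes. With 20 minutes per mask: 4 × 20 + 3 × 5 = 95 minutes.

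**2. Order, if the levels run as listed on every mask**

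The design has 20 × 4 × 4 = 320 cells. Each factor is coded as indicators and the rank of the design matrix is checked.

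| Order | Model | Rank / columns |
|---|---|---|
| Listed | subject + mask + position | 26 / 26 |
| Listed | the same + EPAP | 26 / 29 |
| Listed | the same + EPAP + mask period | 29 / 32 |
| Counterbalanced | subject + mask + position + EPAP | 29 / 29 |
| Counterbalanced | the same + mask period | 32 / 32 |
| Counterbalanced | the same + mask period + first-order carryover | 35 / 35 |

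Under the listed order, adding EPAP raises the rank by nothing: none of its three contrasts can be estimated apart from position.

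Size: EPAP 5 comes three steps after EPAP 0, so a drift of *d* per step adds 3*d* to their difference. For assumed *d* = 0.1, 0.3 and 0.5 mmHg this is 0.3, 0.9 and 1.5 mmHg.

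One kind of drift could still be separated. With linear elapsed time in a four-mask model (subject, mask, EPAP, time; rank 27 of 27), a drift linear over the whole session leaves no bias. A drift that restarts with each mask leaves the full 3*d*.

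**3. Counterbalanced list**

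Take the four rows of a Williams square (level indices 1-2-4-3, 2-3-1-4, 3-4-2-1, 4-1-3-2), with row = (mask + subject) mod 4. Each of the 64 mask × EPAP × position cells then holds 320 / 64 = 5 subjects.

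- Bias in EPAP 5 minus EPAP 0 from additive position effects: 0.
- Variance of that contrast: 2/80 = 0.025 σ², the same as for the fixed order without a time term.
- With a first-order carryover term: about 0.0273 σ².

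**4. Masks compared at the same EPAP**

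These are free of the bias only if drift is equal across masks. Suppose 0.3 mmHg per step on full-face masks only. In the listed order, full-face minus oronasal carries 0, 0.3, 0.6 and 0.9 mmHg at EPAP 0, 2, 4 and 5. Counterbalanced, it carries 0.3 × (0 + 1 + 2 + 3)/4 = 0.45 mmHg at every level.

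**The case against.** **On timing**, the text does not say outright that the clock restarts at each level. That is true, but a single set of readings per mask would leave most levels with no EtCO₂ value, and then neither the aim nor the section 12 comparison could be met. The comfort sentence also points to a per-setting clock. The unseen figure cannot rescue the text: if it shows 20 minutes it contradicts the stated 15, and if it shows 15 the readings do not fit.

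**On order**, the objection is stronger. A procedure figure is where one would expect the EPAP sequence, and content missing from the available text is not thereby missing from the plan. A reader might infer that the plan applies EPAP in ascending order, or that it omits the order altogether. The documents support neither: the values are listed in ascending order, but no sentence says they are applied that way. This part therefore stands only as a conditional.

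**On size**, every drift value is assumed, so no actual bias has been shown. Readings start 4 minutes into a level and must agree to within 20% of their average. Both features limit unsettled readings and carryover from the previous level, but neither would detect a slow trend from one level to the next.

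**Conclusion.** The timing conflict holds on the text as written: 20 minutes are needed against 15 stated, assuming the reading times apply to each level. Which figure is wrong cannot be told from the documents.

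The order point is a conditional, inexpensive improvement. If the levels run as listed on every mask, EPAP is fully aliased with time on mask and the section 12 tests cannot separate the two. If the figure already counterbalances EPAP, only the analysis terms remain of this part.

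Two further inferences would go too far. Same-EPAP mask comparisons are not safe whatever happens: they need equal time-on-mask drift across masks, and section 2 notes that dead space varies between full-face masks. Nor is carryover beyond reach under a counterbalanced list, since a first-order carryover term can be estimated there at a small cost in variance.

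**What to change.** 1. Reconcile the mask time, the number of levels and the reading times, so that each level has a defined slot holding all its EtCO₂ readings and its comfort score. Say that the clock restarts at each level, if it does, and supply the missing unit. Correct the Abstract, section 3 and, if needed, the figure together.
2. State the EPAP order in the text. Unless the figure already provides for it, take the order within each mask from a pre-generated counterbalanced list, such as Williams rows rotated over masks and subjects.
3. Under that list only, analyse EPAP in a repeated-measures model with subject, mask, mask period and within-mask position, with first-order carryover as a sensitivity analysis.
4. If a fixed order is kept, do not fit EPAP together with position, because that model is not estimable. State the order and add the EPAP-time aliasing to section 11.

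**Cost.** No extra subjects or equipment. Settings would no longer change monotonically, and staff must follow a list. A multi-term model would replace the Kruskal-Wallis and Mann-Whitney tests for EtCO₂. Depending on how the timing is reconciled, a session may grow from 75 to 95 minutes.
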